8.2 Pharmacokinetic Parameters

Individual PK parameters will be computed for samples obtained for PK characterization (multiple-dose parameters at Weeks 24, 52, and 104/end of study). Profile intervals will begin at the time of the start of the infusion and continue to the last sample collected on that infusion period. PK parameters will be estimated by standard non-compartment analysis (NCA) methods.

A summary of calculated PK parameters will be presented. All SBC-102 concentrations and calculated PK parameters will be included in data listings. Descriptions and calculations of the PK parameters are presented in the table below.

Parameter	Unit	Description of Parameter	
C _{max}	ng/mI	The maximum serum level observed in units of concentration. Observed	
iig/iiiL		for each subject-dose profiled.	
t _{max}	hr	The time to reach the Cmax in hours to hundredths of the hour. Observed	
	111	for each subject-dose profiled.	
AUC0-t	hr×ng/mL	The Area Under the Concentration curve from the start of the infusion to the last measurable level at weeks 24, 52, and 104/end of study.	
	U	Trapezoidal rule used for estimation.	
AUCtau		The Area Under the Concentration curve from the start of the infusion to the end of the dosing interval.	
	hr×ng/mL	Trapezoidal rule used for estimation but with linear extrapolation to end	
		of dosing interval if needed.	
AUCO-∞		The Area Under the Concentration curve from the start of the infusion	
		extrapolated to infinity (∞) on Day 0.	
		AUC0-t + $[Ct/z]$ where Ct is the last measurable level of a profiled dose	
		interval.	
Z	1/hr	Apparent terminal rate constant calculated from the regression analysis (slope) from the log-transformed measured concentrations on the terminal phase of the time-point concentration curve.	
		Based on slope from linear regression of terminal phase.	
t½	1	Apparent terminal half-life.	
hr		$t^{1/2} = \ln(2)/z.$	
CL mL/hr/kg		Total body clearance.	
		CL =dose/AUC0-t (Weeks 24, 52, and 104/end of study).	
Vz	mI /ka	Volume of distribution after IV infusion.	
IIIL/Kg		Vz = MRTiv x CL where $MRTiv =$ mean residence time.	

Parameters for PK Analysis

For PK parameter estimation, analyte concentrations that are below the limit of quantification (BLQ) will be assigned a value of zero when they precede the first quantifiable sample. BLQ

values embedded between 2 quantifiable data points will be treated as missing. BLQ values occurring after the last quantifiable concentration will be treated as missing data. When consecutive BLQ concentrations are followed by quantifiable concentrations in the terminal portion of the concentration curve, these quantified values will be excluded from the PK analysis by assigning them a value of missing, unless otherwise warranted by the concentration-time profile. No linear interpolation for these missing concentration values will be completed.

Individual PK parameters will be estimated for each subject in the PK analysis set and will be provided in a listing. Actual elapsed sampling time from the start of the infusion will be used for all parameter estimation. Descriptive summaries such as mean, SD, geometric mean, CV%, median, minimum, and maximum of the PK parameters will be presented by dosing cohort.

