3.2.2.5 Pharmacokinetics

The preliminary clinical pharmacokinetics of seblipase alfa will be characterized in study LAL-CL01. Clinical pharmacokinetic data will continue to be collected in this extension study to permit a more robust assessment of sebelipase alfa pharmacokinetics. This will include the steady state pharmacokinetic profile of the qow dosing regimen and an assessment of the impact of ADAs (if any) on sebelipase alfa pharmacokinetics. PK parameters will include maximum observed serum concentration (C_{max}), minimum observed serum concentration (C_{min}), area under the serum concentration-time curve from time zero extrapolated to infinity (AUC_{inf}), terminal elimination half-life ($T_{1/2}$), apparent serum clearance (CL), and steady state volume of distribution (V_{ss}).

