8.1 Plasma Concentration Data

8.1.1 PK Serum Sample Collection Times

PK samples for measurement of SBC-102 serum levels at Weeks 24, 52, and 104/end of study will be collected:

- Immediately pre-dose (within 30 minutes of the start of the infusion).
- At 10(±1), 15(±1), 20(±1), 40(±2), 60(±2) and 90(±2) minutes from the beginning of the infusion and at the end of the infusion (approximately 120 minutes).

At $5(\pm 1)$, $10(\pm 1)$, $20(\pm 1)$, $30(\pm 1)$, $40(\pm 2)$, $60(\pm 2)$ and $120(\pm 2)$ minutes after completion of the infusion.

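### SAP 8.2 gives AUCtau a linear tail over an almost wholly unsampled dosing interval, truncates the AUC used for CL, and labels the protocol's Vss as Vz

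*SAP*

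**What the plan says.** The parameter table in SAP 8.2 sets these rules:

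- **AUCtau**, from the start of infusion to the end of the dosing interval: "Trapezoidal rule used for estimation but with linear extrapolation to end" "of dosing interval if needed".
- **Terminal rate constant** (λz below): a regression slope from "log-transformed measured concentrations on the terminal phase of the time-point concentration curve".
- **AUC0-∞**: AUC0-t plus the last measurable level divided by λz, described as "extrapolated to infinity (∞) on Day 0".
- **Clearance**: "CL =dose/AUC0-t (Weeks 24, 52, and 104/end of study").
- **Volume**: "Vz = MRTiv x CL where" MRTiv is the mean residence time.

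The text after the table treats values below the limit of quantification (BLQ) that follow the last quantifiable level as missing.

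SAP 8.1.1 puts the end "of the infusion (approximately 120 minutes") and the last sample 120 minutes later. Profiles are taken at Weeks 24, 52 and 104.

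Protocol 3.2.2.5 lists Cmax, Cmin, AUCinf, half-life, "apparent serum clearance (CL), and steady state volume of distribution". It lists neither AUCtau nor Vz. SAP 14 records no change to the PK parameters.

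**The concern.** Three rules in one table do not fit together.

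1. The tail of AUCtau is a straight line, while λz and AUC0-∞ treat the terminal phase as exponential. The SAP does not say which line is meant. Two programmers could follow the text and report different values.
2. CL divides the dose by an AUC that stops at the last measurable level, although the table already defines one that does not.
3. Mean residence time multiplied by CL is the formula for Vss. Vz is CL/λz. The protocol's Vss would therefore appear under another parameter's name, and a reader would think it had not been reported.

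Repeat-dose PK is a secondary objective, and AUCinf, CL and Vss are protocol parameters. The table also ties AUC0-∞ to a day on which no profile is taken.

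**Working it through.** **Share of the interval sampled.** Infusion of about 120 min plus 120 min gives 240 min, which matches the last nominal time in SAP 8.1.2. The dosing intervals are 168 h (qw) and 336 h (qow).

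- qw: (168 − 4)/168 = 97.6% unsampled
- qow: (336 − 4)/336 = 98.8% unsampled

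No profile reaches the end of the interval, so the extrapolation always applies.

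**Assumptions for size.** The documents give no half-life and no limit of quantification; Protocol 1.3 expects only a short half-life. I assume one compartment, a 2 h infusion and half-lives of 6 to 60 min. With k = ln 2/half-life and concentrations scaled so that the true AUC0-∞ is 2:

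- C(t) = 1 − e^(−kt) up to 2 h, then (1 − e^(−2k))·e^(−k(t−2))
- Exact AUC0-t = 2 − C(t)/k
- A line from the last level to zero at the interval end τ adds C(t)·(τ − t)/2
- An exponential tail adds C(t)/k, to a close approximation

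**Example: half-life 30 min, qow, sample at 4 h quantifiable.**

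- k = 1.386 per h; C(4 h) = 0.9375 × 0.0625 = 0.0586
- AUC0-4h = 2 − 0.0586/1.386 = 1.958
- Linear tail = 0.0586 × 332/2 = 9.727; exponential tail = 0.042
- AUCtau/true = (1.958 + 9.727)/2 = 5.84
- CL error from truncation alone = 2/1.958 − 1 = 2.2%

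The last two columns of the table use the linear trapezoidal rule at the scheduled times, as the SAP specifies for AUC0-t. They therefore include integration error as well as truncation.

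| Half-life (min) | AUCtau/true, qw | AUCtau/true, qow | CL error, dose/AUC0-t | CL error, dose/AUC0-∞ |
|---|---|---|---|---|
| 6 | 1.00 | 1.00 | +0.46% | +0.46% |
| 10 | 1.01 | 1.02 | +0.20% | +0.20% |
| 15 | 1.16 | 1.32 | −0.11% | −0.18% |
| 20 | 1.63 | 2.27 | −0.07% | −0.44% |
| 25 | 2.41 | 3.86 | +0.48% | −0.56% |
| 30 | 3.38 | 5.84 | +1.55% | −0.59% |
| 60 | 8.55 | 16.43 | +15.2% | −0.30% |

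All rows assume that the 4 h sample is quantifiable. A log-linear tail gives an AUCtau ratio of 1.000 in every row. That follows from the assumed model and is not independent evidence.

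**Effect of dropping trailing BLQ values.** The line then starts at an earlier and higher level. I let Cmax divided by the quantification limit run from 50 to 10,000. The qow ratio spans 1.1 to 3.6 at 6 min, 1.0 to 6.2 at 10 min and 1.3 to 6.2 at 15 min.

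The upper value at 10 min arises as follows. At a limit of Cmax/50, the last quantifiable sample is 40 min after the infusion (t = 2.667 h), at 2^(−4) = 0.0625 of Cmax. The line adds about 0.0625 × 333.3/2 = 10.4 to an AUC0-t of 1.985, and 12.4/2 = 6.2.

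Over the same range, truncation alone raises CL by at most 1.1% at 6, 10 and 15 min.

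**Volume.** Vss = CL × MRT, and Vz = CL/λz. The SAP computes the first and prints the second name.

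**The case against.** **Linear may mean log-linear.** The table describes λz as a linear regression on logged concentrations, and SAP 8.2 invokes standard non-compartmental methods. On that reading AUCtau is correct. This is possible, but the AUCtau row does not say so, and a general reference to standard methods does not override an explicit rule beside it.

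**The half-life is short, so the tail is nothing.** This stands in part. If the 4 h sample is quantifiable at a half-life of 10 min or less, the ratio is 1.00 to 1.02. The BLQ rule removes that protection, so no half-life can be named below which the rule is safe.

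**The model is simple.** This also stands. Protocol 1.3 reports that uptake in rats appears saturable, which a linear one-compartment model ignores. The sizes are illustrations.

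**The CL choice is defensible.** A reader might infer that dividing by AUC0-t always biases CL upward. Truncation on its own does, but the trapezoidal rule partly offsets it, and the net error is slightly negative at 15 and 20 min. From 15 to 25 min, AUC0-∞ is marginally further from the truth, with both errors below 0.6%. The case for changing CL rests on longer half-lives.

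**Other inferences to avoid.** A reader might take the 98.8% as a share of exposure. It is a share of time; the true area beyond 4 h is 0.07% of AUC at 15 min and 2.1% at 30 min. A reader might also extend the slope of the last two samples and obtain a negative AUCtau, but the SAP does not prescribe that line. Nor does the Vz label imply a wrong value.

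**Conclusion.** The point holds as a low-priority correction. The inconsistency in AUCtau, the truncated denominator for CL and the mislabelled volume can all be read from SAP 8.2 without assuming a half-life.

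Their size does depend on assumption. With a line to zero, the qow AUCtau runs from about 1.0 to 16 times the true value over half-lives of 6 to 60 min, and it can be several-fold too large even at 6 to 10 min once trailing BLQ values are dropped. With all samples quantifiable, the net CL error is within about 0.5% from 6 to 25 min, about +1.5% at 30 min and +15% at 60 min; its direction is not fixed. The Vz label has no numeric effect, and the Day 0 wording reads as a stray phrase.

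Consequences are limited. PK is descriptive in up to 9 subjects. AUCtau is not a protocol parameter and feeds no other parameter. AUC0-∞, which is a protocol parameter, has a sound formula.

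**What to change.** 1. Delete AUCtau, or state that its tail is log-linear with λz. Deletion loses nothing at these half-lives, because a log-linear AUCtau equals AUC0-∞ for practical purposes.
2. Compute CL as dose/AUC0-∞ at Weeks 24, 52 and 104, report the percentage of AUC extrapolated, and remove the reference to Day 0. Still report AUC0-t for profiles where λz cannot be estimated.
3. Relabel the volume Vss = CL × MRT, with MRT = AUMC0-∞/AUC0-∞ minus half the actual infusion time (AUMC is the area under the first-moment curve). Do not keep the name by switching the formula to CL/λz, because the protocol asks for Vss.

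The cost is a few edits to the SAP table and standard software settings, with no new samples. The drawback is that CL and Vss will be missing for profiles without an estimable λz, which matters with at most 9 subjects.

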8.9 Pharmacokinetics

 C_{max} and C_{min} will be recorded from direct observation, and other PK parameters will be derived by non-compartmental analysis. Pharmacokinetics will be characterized using the PK Analysis Set. All PK parameters will be summarized by dosing by dosing regimen.

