2.2.3 Pharmacokinetic Endpoints

The PK endpoints are the multiple-dose (Weeks 24, 52, and 104) parameters estimated from the PK sampling times and serum SBC-102 concentrations for each dose profiled.

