4.4 Data Reporting by Cohort

For this study, results will be reported by cohort and overall. A subject's dose cohort will be defined by the dose of longest duration, i.e., by the subject's every-other-week dose.

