8.1.4 PK Serum Sample Presentations

PK concentration data will be listed as received from the bioanalytical laboratory along with dosing dates and times, scheduled sampling times, elapsed time from start of the infusion, lab reported concentration, and deviation from the scheduled sampling times in minutes.

PK concentration data will be summarized by dose at the time of the infusion (rather than cohort) and profile week (24, 52, and 104) using the modified sampling schedule times.

Observed values of SBC-102 concentrations will be summarized by dosing regimen and plotted over time. Descriptive statistics will include mean, SD, minimum, median, maximum, CV% and geometric mean. SBC-102 concentrations at pre-dose times will be set to zero and a footnote added if this situation occurs.

Figures will be provided for each subject's concentration-time data and for mean data at each dose and profile week. Individual concentration-time figures will contain Weeks 24, 52, and 104 profiles plotted in the same figure with origin for both lines being the start of the infusion. Mean concentrations will be illustrated in 3 figures (Weeks 24, 52, and 104) with different plots for different doses (since subjects may be changing doses during the study, there may be up to 3 dose levels. All figures will be presented in linear and semi-log scale.. Based on a review of the final data, some adjustments may be made to the graphical presentations and additional figures may be created to more fully present the data.

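### SAP 8.2 summarizes PK parameters by one fixed cohort label per subject, while SAP 8.1.4 groups the concentrations from the same profiles by the dose at the infusion

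*SAP*

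**What the plan says.** On concentrations, SAP 8.1.4 states "PK concentration data will be summarized by dose at the time of the infusion (rather than cohort") and by profile week. In describing the mean plots it gives the reason: "since subjects may be changing doses during the study, there may be up to 3 dose levels". The same section also says that observed concentrations are summarized by dosing regimen, so it uses two grouping terms.

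On the parameters derived from those profiles, SAP 8.2 says that the summaries "of the PK parameters will be presented by dosing cohort". SAP 4.4 fixes what that means for each subject: the "dose cohort will be defined by the dose of longest duration", which it then equates with the subject's every-other-week dose. SAP Section 14 item 4 repeats this rule as a change from the protocol that applies to tabulations in general.

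Protocol 8.9 reads: "All PK parameters will be summarized by dosing by dosing regimen" (the repeated words are in the original). Protocol 8.1 explains that regimen means dose together with dosing frequency. Protocol 6.1.1 permits two escalations after at least 12 weeks of treatment: 1 to 3 mg/kg qow, and 3 mg/kg qow to 3 mg/kg qw.

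**The concern.** Cmax and AUC depend on the dose infused. A cohort label describes a subject's whole time on study, not the infusion that was profiled. Section 8.1.4 recognizes this and avoids cohort for the concentrations; Section 8.2 returns to it for the parameters. Followed as written, the same Week 24 profile can stand under 1 mg/kg in the concentration table and under 3 mg/kg in the Cmax and AUC table.

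Repeat-dose PK is a secondary objective. Protocol 3.2.2.5 says of the PK assessment: "This will include the steady state pharmacokinetic profile of the qow dosing regimen". A column that mixes 1 and 3 mg/kg profiles does not describe either regimen, and the CV% and geometric mean that 8.2 reports would carry the mixing as if it were between-subject variation.

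**Working it through.** The plan gives no figure to reproduce: there is no power calculation and no formal test. The check applies the grouping rules to dose histories that the protocol permits.

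**Inputs.** Profiles at Weeks 24, 52 and 104 (SAP 2.2.3, 8.2). Every-other-week dosing from Week 6 (SAP 3.1). Escalation after Week 12 (protocol 6.1.1). End of treatment F = 156 weeks (SAP 3.1, up to 3 years) or 260 weeks (protocol 6.1, about 5 years). At most 9 subjects (protocol 4.2). Let E be the week of the first 3 mg/kg qow infusion; a profile at or after E is a 3 mg/kg profile. The documents do not give actual values of E.

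**Step 1: any single label, 1 to 3 mg/kg qow.**
- E from 25 to 52: Week 24 is at 1 mg/kg, Weeks 52 and 104 at 3 mg/kg. Label 3 misplaces 1 profile; label 1 misplaces 2.
- E from 53 to 104: Weeks 24 and 52 are at 1 mg/kg, Week 104 at 3 mg/kg. Label 3 misplaces 2; label 1 misplaces 1.

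No choice of label avoids the error in this window.

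**Step 2: the label that longest duration gives.** Time at 1 mg/kg is E − 6 (0.35 mg/kg starter) or E − 1 (1 mg/kg starter, weekly weeks counted). Time at 3 mg/kg is F − E.
- E = 30: 24 or 29 weeks against 126 (F = 156) or 230 (F = 260). Label 3; Week 24 misplaced.
- E = 60: 54 or 59 against 96 or 200. Label 3; Weeks 24 and 52 misplaced.
- E = 90: 84 or 89 against 66 or 170. With F = 156 the label is 1 and Week 104 is misplaced; with F = 260 the label is 3 and Weeks 24 and 52 are misplaced.

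Outside the window, a rise at Weeks 13 to 24 misplaces none. A rise after Week 104 misplaces none with F = 156. With F = 260 the label is still 3 while 260 − E > E − 6 (E up to 132) or 260 − E > E − 1 (E up to 130), so a rise from Week 105 to Week 130 or 132 misplaces all three, and a later rise none.

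**Step 3: size of the mixing (illustration).** Suppose exposure varies as dose to the power b, and k of n profiles in a 3 mg/kg column were taken at 1 mg/kg. With r = 3^(−b):
- mean relative to 3 mg/kg = [(n − k) + k·r] / n
- SD = (1 − r)·√[k(n − k) / (n(n − 1))]

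For b = 1 and n = 5:
- k = 1: mean (4 + 1/3)/5 = 0.867; SD 0.667 × √(4/20) = 0.298; CV 0.298/0.867 = 34%.
- k = 2: mean (3 + 2/3)/5 = 0.733; SD 0.667 × √(6/20) = 0.365; CV 0.365/0.733 = 50%.

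For n from 4 to 8 and b from 0.8 to 1.2, the mean is 82% to 93% with one misplaced profile (CV 22% to 45%) and 63% to 85% with two (CV 32% to 67%). Both n and b are assumptions. A 3 mg/kg profile in a 1 mg/kg column would push the mean up instead.

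**Step 4: the cohort definition in SAP 4.4.** Take a subject on 1 mg/kg qow from Week 6, 3 mg/kg qow from Week 50 and 3 mg/kg qw from Week 78. The times are 50 − 6 = 44 weeks, 78 − 50 = 28 weeks, and 156 − 78 = 78 or 260 − 78 = 182 weeks. This subject has two every-other-week doses, so that clause of 4.4 does not pick one. The regimen of longest duration is weekly. For a 3 mg/kg starter moved from qow to weekly at Week E, weekly time exceeds qow time when F − E > E − 6, that is up to Week 80 (F = 156) or Week 132 (F = 260).

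**The case against.** The strongest reply is that the change is disclosed and little is lost. Protocol 8.1 allows exceptions to its default tabulation, Section 14 item 4 declares the cohort rule, individual PK parameters are listed, concentrations and exposure are summarized by dose, and no between-cohort test is planned. All of that stands and limits the consequence. It does not explain why two tables from the same profiles are grouped differently, and Section 14 does not mention the exception made in 8.1.4.

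A second reply is that the SAP's phrases "parameters estimated from the PK sampling times and serum SBC-102 concentrations for each dose profiled" (2.2.3) and "for each subject-dose profiled" (8.2) only say how an individual value is derived. That is fair: they fit grouping by infusion better than grouping by cohort, but they do not fix the grouping of summaries.

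Third, the size is hypothetical. No dose change is documented, dose proportionality is assumed, and protocol 1.3 reports apparently saturable uptake in rats. This is why a range is shown and the figures are called an illustration.

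Three stronger readings are tempting and not supported:
- *The cohort rule contradicts itself.* If dose means mg/kg, as the count of dose levels in 8.1.4 suggests, a 3 qow to 3 qw change keeps the 3 mg/kg label and nothing conflicts. In the Week 50 and 78 history, 3 mg/kg totals 28 + 78 = 106 or 28 + 182 = 210 weeks against 44, and it is also one of that subject's qow doses. A clash in mg/kg appears only if one reads 4.4 as naming the longest qow dose, which it does not say.
- *Merging weekly and qow profiles at 3 mg/kg distorts Cmax or AUC.* Nothing in the documents shows this; protocol 1.3 and 1.5.1 describe rapid clearance and a short half-life.
- *Profile weeks will be pooled.* The summary sentence of 8.2 names no week, but the section computes parameters at Weeks 24, 52 and 104.

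**Conclusion.** The mismatch between SAP 8.1.4 and 8.2 is explicit in the text, and 8.2 also departs from protocol 8.9. For a rise from 1 to 3 mg/kg qow at Weeks 25 to 104, 1 or 2 of 3 profiles per such subject are summarized under a dose not given, whichever label is used; this needs no assumption beyond the profile weeks. The 87% and 73% means rest on proportionality and on five profiles in the column. Under proportionality, weight-normalized CL, volume and half-life do not depend on dose, so the problem lies mainly in Cmax and AUC. The number of subjects affected is unknown and could be zero.

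The SAP 4.4 wording is a secondary ambiguity. The every-other-week dose is not unique after both 1 and 3 mg/kg qow, and it disagrees with the longest-duration clause only if dose means regimen and weekly dosing lasted longest. The point concerns grouping and labelling alone; it takes no view on any dose or escalation rule.

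**What to change.** 1. Replace the last sentence of SAP 8.2 with wording such as: *PK parameters will be summarized by the actual dosing regimen (mg/kg and frequency) at the profiled infusion and by profile week (24, 52, 104), using mean, SD, geometric mean, CV%, median, minimum and maximum.*
2. Use that one term in SAP 8.1.4 in place of both dose and dosing regimen, so that concentrations and parameters share the same columns.
3. Except PK from Section 14 item 4.
4. In SAP 4.4 and Section 14 item 4, state whether cohort means mg/kg or regimen, and which label applies to a subject who received both 1 and 3 mg/kg qow. Reconcile the treatment duration (up to 3 years in SAP 3.1, about 5 years in protocol 6.1), because it can change the longest-duration label, as in the Week 90 example.

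The cost is a few sentences and re-programming of the PK tables. SAP 8.1.3 already brings actual dose amounts and infusion times into the PK dataset. The downside is very small cells: with at most 9 subjects, some regimen-by-week columns may hold one or two profiles and are then better read from the listing. Adverse event tables by regimen would be a separate, optional request and are not part of this point.
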